2.2.5 SAFETY PHARMACOLOGY

During safety pharmacology studies with the microcrystalline free base formulation, no neurobehavioral effects were observed in male rats treated with MBX-2982. No changes in QT interval were observed in an oral safety pharmacology study designed to assess cardiovascular effects in conscious telemeterized dogs or in a general toxicology study conducted in dogs. During the conscious telemeterized dog study, minimal hemodynamic changes, considered physiologically insignificant, were observed at the highest dosages (300 and 1000 mg/kg).

To further enable human studies with the anticipated improvements in exposure due to the SDD formulation of MBX-2982, an additional oral safety pharmacology study was conducted with the SDD formulation to assess cardiovascular effects in conscious telemeterized dogs with greater exposure to MBX-2982. No test article-related changes in electrophysiology parameters, including QT interval, were observed in this second study at the top dose (100 mg/kg), which was associated with a Cmax of 13.2 µg/mL. This represents an approximate 5.1-fold increase over the previous no effect Cmax achieved at 1000 mg/kg with the microcrystalline free base formulation in the first dog cardiovascular safety study. Except for minor and transient higher heart rates compared to control (but not to baseline), there were no hemodynamic changes in the oral safety pharmacology study with the SDD formulation.

In vitro assays were performed to evaluate the effects of MBX-2982 on cardiac ion channel and action potential durations (APD). In the first assay, effects of MBX-2982 concentrations on the IKr (cardiac delayed rectifier repolarizing current) channel were assessed. In this study, the IKr channel was inhibited by MBX-2982 in a concentration-dependent manner with a 50% inhibitory concentration (IC50) of 1.16 µM (0.52 µg/mL). In the APD assay, MBX-2982 produced no effect on the action potential at a normal stimulation rate. At the highest concentration, 20 µM (9.0 µg/mL), a slight but statistically significant APD90 prolongation occurred under stimulation rates corresponding to bradycardia and tachycardia. As noted above, no in vivo cardiac effects or QT prolongation were observed in the telemeterized dog studies or during the 4-week repeat dose dog study. MBX-2982 was not genotoxic in any of the systems evaluated

[figure not shown]

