2.2.6 HUMAN EXPERIENCE

Phase 1 and Phase 2 Studies in Patients

In early human studies, as earlier noted, undertaken with the original intent of exploring a potential for treating T2DM, MBX-2982 consistently lowered fasting plasma glucose (FPG) and glucose excursion following a mixed meal tolerance test (MMTT) and an oral glucose tolerance test (OGTT). During a graded glucose infusion, MBX-2982 attenuated hyperglycemia and enhanced glucose-sensitive insulin secretion. Across the three completed Phase 1 studies, MBX-2982 had variable effects on other biomarkers such as GLP-1 and glucagon during an MMTT or OGTT. Four Phase 1 studies and a 28-day Phase 2 human study have been completed and there has been no safety, pharmacokinetic (PK) or tolerability concerns with MBX-2982 dosing. A Phase 2 study evaluated sitagliptin as a comparator to MBX-2982. These data

suggested that there may be additional benefit on glucose homeostasis if MBX-2982 is combined with sitagliptin.

MBX-2982 was studied in 3 formulations in the clinic. A microcrystalline free base formulation (MBX-2982), a spray dried dispersion (MBX-2982 SDD) formulation and an HCl salt formulation (MBX-2982A). The HCl salt, which had an exposure of 54,600 ng*ml/hr., was deemed the formulation best suited to take forward in development. Administration of MBX-2982 HCl salt formulation in single and multiple doses of 100 mg and 300 mg capsules have been safe and well tolerated.

	100 mg (Day 4)	300 mg (Day 4)	1000 mg* (Day 1)
C_{\max} (ng/mL)	365	437	818
T_{\max}	4.1	1.7	3.0
$t_{1/2}$	19.2	29.1	18.4
AUC_{0-24} (ng*h/mL)	6098	6998	7924

Table 1 and Figure 1: Data from the first-in-human study (*Protocol M2982-10712*)

Micronized free base formulation

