2.3.3.2 MITIGATION OF POTENTIAL RISKS ASSOCIATED WITH THE INVESTIGATIONAL DRUG

The drug was well tolerated and had a very low order of toxicity at the proposed concentration in previous human studies and at higher concentrations in animal models.

It is important that women of childbearing potential receiving MBX-2982 in early investigational development do not become pregnant for at least 2 weeks after the last dose. As a precaution, women of childbearing potential receiving MBX-2982 should use at least one medically accepted method of contraception with >99% effectiveness when used consistently and correctly. As the induction potential of MBX-2982 on CYP enzymes is not clear. Given that the effectiveness of hormonal contraceptives can be reduced by CYP enzyme inducers, we recommend that study subjects who are women of childbearing potential use a barrier method during the study to prevent unintended pregnancy. In addition, it is important that partners of male subjects receiving MBX-2982 should not become pregnant during the study. As a precaution, male subjects receiving MBX-2982 should use dual method of contraceptive use: medically accepted contraception (e.g., condoms w/spermicide), or their partner should also use a medically accepted form of contraception along with condoms during this period.

Although the studies in humans did not show clinically relevant ECG alterations, in vitro studies showed potential for QT prolongation. For this reason, ECGs will be performed on Visits 4, 5, 7, 8 during investigational medication treatment, in addition to the screening Visit 1. At visits 5 and 8, the ECG will be performed during the meal test at the time of predicted drug concentration peak 180 min after taking the medication. The QTcF will be manually calculated for each ECG.

Elevated TSH levels were reported in one of the human studies but not confirmed in others. TSH and FT4 have been added to the safety measures at visit 5 and visit 8 during study treatment.

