7.2 PARTICIPANT DISCONTINUATION/WITHDRAWAL FROM THE STUDY

7.2.1 INVESTIGATOR WITHDRAWAL OF SUBJECTS

The participation in this study may be stopped at any time by the study PI without the participant's consent because:

- The study Medical investigator thinks it necessary for subject's health or safety;
- Participant has not followed study instructions;
- The AdventHealth Translational Research Institute has stopped the study; or
- Administrative reasons require the participant's withdrawal.

A participant will be discontinued/withdrawn if the following occur during study treatment:

- Any episode of Level 3 hypoglycemia according to the ADA classification
- Any episode of Diabetes Ketoacidosis (DKA) defined by serum or urine ketones greater than the upper limit of normal range and serum bicarbonate <15 mmol/l or blood pH <7.3 without a satisfactory alternative cause for anion-gap acidosis
- Persistent glycemia aberration defined as:
 - Hypoglycemia: ≥ 3 episodes per week of level 2 hypoglycemia (blood glucose ≤ 54 mg/dL, [3.0 mmol/L]) not prevented by appropriate insulin dose adjustments.
 - Hyperglycemia: Level 2 fasting hyperglycemia (blood glucose ≥ 250 mg/dL [13.9 mmol/L]) in 4/7 days not prevented by appropriate insulin dose adjustments
- Increase in QTcF to >500 ms or >60 ms over baseline confirmed in at least two ECGs

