8.1.5 VISIT 4 – FOLLOW UP VISIT/ DAY 7±2 (OUTPATIENT, 1-1.5 HOURS)

The visit will be done at the TRI or ProSciento.

The following procedures will be completed for participants with T1DM:

- CGM management and data review
- Review knowledge of insulin dose adjustments, ketone testing and sick day management, hypoglycemia symptoms and treatment
- Fingerstick blood glucose/personal CGM data, insulin and study medication log review
- AE/Con-med Assessment
- ECG

Data from the CGM will be analyzed.

8.1.6 VISIT 5 – PERIOD 1/ DAY 13-14+5 (T1DM COHORT) (INPATIENT, 2 DAYS) OR WITHIN 28 DAYS AFTER SCREENING (HEALTHY COHORT)

The visit will be done at the TRI or ProSciento.

The scheduled day of intervention is valid for participants with T1DM.

Healthy participants will undergo the same procedures of this visit any time between 7 and 28 days after screening

Because moderate and severe episodes of hypoglycemia can have a transient effect of at least several days to dampen counter-regulatory responses to a subsequent episode of hypoglycemia (12, 15, 21) the clamp procedure may need to be re-scheduled so that a window of at least 5 days without moderate or severe episodes of hypoglycemia (blood glucose <55 mg/dl) precedes the clamp study (and supplemental study medication can be provided under such circumstances). Subjects will be admitted in the fasting state (10hours) to the Research Center in the morning the day prior to the clamp study (which will be conducted on the following morning).

The following procedures will be completed in participants with T1DM and in healthy participants:

- Physical exam
- Height and weight measurement
- BMI calculation
- Vital signs (Heart rate x 2, blood pressure x 2, respirations, temperature) on each day of CRU staying
- ECG during the meal test
- AE/Con-med Assessment
- Follow up labs (fasting for at least 10 hours, water is permitted): CBC, CMP, HbA1c, lipid panel, thyroid function.
- Urine pregnancy test
- Standard meal challenge with pre- and post-meal blood draw to measure glucose, glucagon, total GLP-1, total GIP, and blood study medication levels (GRP119 PK)
- Overnight IV infusion of regular insulin (T1DM participants only)
- Euglycemic and hypoglycemic clamp
- CGM management and data review
- Fingerstick blood glucose/personal CGM data, ketone, insulin and study medication log review
(T1DM participants only)
- Adherence to study drug will be evaluated (T1DM participants only)
- Blood for archive
- Urine for archive

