- Comprehensive metabolic panel (CMP) (Anion Gap, Albumin, Globulin, A/G Ratio, Alkaline Phosphatase, ALT, AST, Bilirubin Total, BUN, Creatinine, eGFR by CKD-EPI, Calcium, Chloride, CO₂, Creatinine, Glucose, Potassium, Sodium, Total Protein)
- HbA1C
- lipid panel (Total Cholesterol, HDL, LDL, Chol/HDL ratio, LDL/HDL Ratio, Non-HDL Cholesterol, Triglycerides, VLDL, CHD Risk Assessment)
- Thyroid function test: thyroid stimulating hormone (TSH) and free T4• urine pregnancy test, for female subjects of childbearing potential

The **total amount of blood** required for the study will be about 547.1 ml during the whole study.

Vital Sign Measurements

Measurement of vital signs will include heart rate (HR), blood pressure (BP), respirations and temperature will be measured sitting for at least 5 min.

Electrocardiograms (ECGs): ECG will be done at screening and during intervention periods at visits 4 and 5, and visits 7 and 8. At visits 5 and 8, the ECG will be performed during the meal test at the time of predicted drug concentration peak 180 min after taking the medication. The QTcF will be manually calculated for each ECG.

Fingerstick glucose and ketone measures

Fingerstick glucose and/or monitoring of personal CGM will be encouraged to measure/monitor at home by the participant before meals and at bedtime.

Participants will be instructed to check urinary ketones and in case of symptoms indicative of ketoacidosis or blood glucose >250 mg/dl.

Counseling procedures and Insulin dose adjustments

The participants will be instructed to check their blood glucose with a glucometer/personal CGM device before each meal and at bedtime. The participants may be instructed on insulin dose adjustments, ketone testing and sick day management, hypoglycemia symptoms and treatment.

Assessment of adverse events. See below.

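### The Visit 4 and Visit 7 ECGs, ordered because of an in vitro QT signal, are not tied to the dose, so a rise at peak could be picked up about a week late

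*Combined protocol and SAP*

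**What the plan says.** Section 2.3.3.2 reports no clinically relevant ECG changes in human studies but notes that "in vitro studies showed potential for QT prolongation". It then says "For this reason, ECGs will be performed on Visits 4, 5, 7, 8 during investigational medication treatment", in addition to screening. Section 9 (Electrocardiograms) repeats the list: "ECG will be done at screening and during intervention periods at visits 4 and 5, and visits 7 and 8".

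Both sections then time two of these four ECGs. At Visits 5 and 8 the recording is made during the meal test, "at the time of predicted drug concentration peak 180 min after taking the medication". Section 8.2 adds a window of ±5 minutes.

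For Visits 4 and 7, the Schedule of Activities (1.3) and the visit lists (8.1.5 and 8.1.9) show an ECG and nothing more. Both are outpatient visits of 1-1.5 hours, on Day 7±2 and Day 35±2. Study drug is self-administered once daily after the morning meal (6.1.2.4). The medication log is reviewed at these visits, but the plan does not say whether it holds clock times. Drug levels are measured only at Visits 5 and 8.

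Section 7.2.1 makes the following a reason for withdrawal: "Increase in QTcF to >500 ms or >60 ms over baseline confirmed in at least two ECGs".

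**The concern.** By fixing two ECGs at the predicted peak, the plan treats time since dose as relevant to QTcF. Section 2.2.5 gives the reason: in vitro, "the IKr channel was inhibited by MBX-2982 in a concentration-dependent manner". The same reason applies to the other two ECGs, yet nothing prevents their being recorded before that day's dose.

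The two untimed ECGs are also the ones that could prompt action while much of the course remains. The peak-timed ECG falls on Day 13 or Day 41, with the last dose on the following morning. Each period has exactly two scheduled on-treatment ECGs, one untimed and one at peak, so the pair that bears on the two-ECG withdrawal criterion is not like-for-like. With no drug level taken at Visits 4 and 7, and no stated record of dose and ECG times, a low reading there could not be interpreted afterwards.

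**Working it through.** The plan states no figure to reproduce. The check has four steps.

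**1. Is there a dose link elsewhere?** Sections 1.3, 2.3.3.2, 8.1.5, 8.1.9, 8.2 and 9 were compared. Only Visits 5 and 8 carry a post-dose time. A 180-minute interval does not fit inside a 1-1.5 hour visit if the dose is taken there, so the timing depends on when the participant dosed at home.

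**2. Doses left and possible delay.** The last dose of a 14-day course is on Day 14.
- Doses left after Visit 4: 14 - 7 = 7; for ±2 days, 14 - 9 = 5 to 14 - 5 = 9. Visit 7 gives the same counts from Day 42.
- Doses left after the peak-timed ECG: 14 - 13 = 1.
- Gap between the two ECGs: 13 - 7 = 6 days (13 - 9 = 4 to 13 - 5 = 8). If the +5 day window moves admission to Day 18, the gap can reach 18 - 5 = 13 days.

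**3. Worst case: ECG just before the dose.** Inputs are the half-lives in Table 1 (2.2.6): 19.2, 29.1 and 18.4 for 100, 300 and 1000 mg. Hours are assumed, since no unit is printed. The table is for the micronized free base and is assumed to apply to the HCl salt. From 3 h to 24 h after a dose is 21 h, so the fraction left is 0.5^(21/t½).

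| t½ (h) | Fraction of 3-h level | 60 ms at peak reads as |
|---|---|---|
| 18.4 | 0.453 | 27.2 ms |
| 19.2 | 0.469 | 28.1 ms |
| 29.1 | 0.606 | 36.4 ms |

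The last column assumes that QTcF change is proportional to concentration. Conversely, a pre-dose reading of 60 ms would need a peak rise of 60/0.606 = 99 ms to 60/0.453 = 132 ms.

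**4. Other times after the dose.** A one-compartment oral model at steady state with 24-hour dosing was used, with ke = ln2/t½ and ka solved from ln(ka/ke)/(ka - ke) = Tmax. Table 1 gives Tmax as 4.1, 1.7 and 3.0 (hours assumed), so ka = 0.79, 2.84 and 1.19 per hour. Concentration as a share of the steady-state peak:

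| Time after dose | 100 mg | 300 mg | 1000 mg |
|---|---|---|---|
| 0.5 h | 0.70 | 0.92 | 0.74 |
| 2 h | 0.96 | 0.99 | 0.99 |
| 3 h | 1.00 | 0.97 | 1.00 |
| 5 h | 0.97 | 0.93 | 0.94 |
| 6 h | 0.95 | 0.90 | 0.91 |
| 8 h | 0.89 | 0.86 | 0.84 |
| 24 h (pre-dose) | 0.50 | 0.59 | 0.46 |

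At 5-8 h the share is 84-97%, so a 60 ms rise would read 60 × 0.84 = 50 ms to 60 × 0.97 = 58 ms. The large loss arises mainly when the ECG precedes the dose.

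Accumulation is not the limit. The steady-state fraction 1 - 0.5^(24 × days/t½) is already 0.943-0.989 at Day 5. Time since dose is the main uncontrolled factor.

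**The case against.** The strongest reply is that the plan already has an ECG at predicted peak in each period, at steady state. That stands. A reader might infer that a QTcF rise could go undetected, but the plan does not support this: a rise at peak would more likely be found late than missed. Only one of Visits 4 and 7 falls on active drug for a given participant, so the exposure to delay is one visit each.

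It is also fair that Visits 4 and 7 have no fasting blood draw and no instruction to hold the dose. A reading some hours after breakfast is at least as plausible as a pre-dose one, and it would lose little. The 27-36 ms range is the worst case, not the expected one.

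A reader might further infer a high QT risk by setting the exposure statement in section 2.2.6 ("The HCl salt, which had an exposure of 54,600 ng*ml/hr") against the IKr IC50 of 0.52 µg/mL. That comparison should not be made. The unit as printed is not that of an AUC, no dose or interval is given, and plasma levels of total drug cannot be set against an in vitro value without protein-binding data, which the documents do not give. The same documents report no QT change in telemetered dogs at a Cmax of 13.2 µg/mL, about 25 times the IC50 (13.2/0.52). They also report no action-potential effect at a normal stimulation rate (2.2.5), no imbalance of QTc prolongation in humans (2.2.7.1) and no clinically relevant ECG alterations (2.3.3.2). One limit on that reassurance is that the 28-day study used the SDD formulation up to 300 mg, and section 2.2.6.1 lists the 600 mg HCl salt only in a single-dose study.

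Nor do the documents show that the two-ECG criterion cannot work. They do not exclude an unscheduled repeat, and the investigator may withdraw a participant for safety at any time. QTcF is not an endpoint, and no comparison of QTcF between visits is planned.

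Finally, the ±5 minute window cannot sensibly be carried over to a dose taken at home. This is correct and shapes the fix.

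**Conclusion.** The point holds as a cheap improvement. The passages do not contradict each other; the plan leaves two of four ECGs, all ordered for the same reason, without a dose time. These two are the only ECGs with about 7 doses (5 to 9) still to come.

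The consequence is possible detection about a week late, at one visit per participant. If the ECG is taken before the dose, it sees about 45-61% of the 3-hour level, and a 60 ms peak rise reads about 27-36 ms. If it is taken 5-8 h after the dose, the loss is small.

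These figures assume that free-base half-lives and Tmax apply to the 600 mg HCl salt, that Table 1 is in hours, that a one-compartment model is adequate, and that QTcF change is proportional to concentration. The documents give no half-life or Tmax for 600 mg of the HCl salt, so the percentages are indicative. The QT signal is in vitro only.

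**What to change.** In sections 2.3.3.2, 8.1.5 (Visit 4), 8.1.9 (Visit 7) and 9 (Electrocardiograms), state that the Visit 4 and 7 appointments are booked so that the ECG already planned is taken after that day's home dose, around the predicted peak that the plan uses at Visits 5 and 8. Allow a practical window wider than ±5 minutes, because the dose is self-taken and the visit lasts 1-1.5 hours. High precision is not needed: at the times modelled from 2 to 6 h the level stays at 90% of peak or more. Record the clock time of the dose and of the ECG on the CRF at all four visits.

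The cost is wording in four places, two CRF time fields, less flexible appointments, and reliance on a self-reported dose time. No extra ECG, visit or staff is needed, and no dose or withdrawal threshold changes.

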3 OBJECTIVES AND ENDPOINTS

Primary Objectives and Endpoints	
Objective	Endpoint
To compare (relative to placebo treatment) the effect of MBX-2982, a GPR119 agonist, on glucagon counter-regulatory responses to insulin-induced hypoglycemia in subjects with T1DM.	Maximal glucagon concentration during hypoglycemia. Total area under the curve (AUC) for glucagon during hypoglycemia. Incremental AUC for glucagon during hypoglycemia (above baseline levels during euglycemia)
Secondary Objectives and Endpoints	
Objectives	Endpoint
To determine whether MBX-2982, through its effect upon glucagon counter-regulation, increases hepatic glucose production (HGP) during insulin-induced hypoglycemia and during recovery to euglycemia in subjects with T1D relative to placebo treatment.	HGP during insulin-induced hypoglycemia. HGP during recovery from insulin-induced hypoglycemia to euglycemia.
To determine whether MBX-2982 reduces time of recovery from hypoglycemia to euglycemia in T1DM relative to placebo treatment	Time of recovery from hypoglycemia (time to reach 85 mg/dL).
To determine whether there is any effect of MBX-2982 upon other key counter-regulatory hormones in T1D relative to placebo treatment	Plasma levels of counter regulatory hormones during hypoglycemia including epinephrine, cortisol, GH.
To compare the glucagon counter-regulatory response in healthy (non-diabetic) volunteers during insulin-induced hypoglycemia to that of subjects with T1DM treated with MBX-2982 and placebo.	Total area under the curve (AUC) for glucagon during hypoglycemia Incremental AUC for glucagon during hypoglycemia (above baseline levels during euglycemia) Plasma levels of counter regulatory hormones during hypoglycemia including epinephrine, cortisol, GH.
To compare time to recovery to euglycemia from insulin-induced hypoglycemia in healthy (non-diabetic) volunteers to that of subjects with T1DM treated with MBX-2982 and placebo	Time of recovery from hypoglycemia.
To compare the hepatic glucose production response to insulin-induced hypoglycemia in healthy (non-diabetic) volunteers to that of subjects with T1DM treated with MBX-2982 and placebo	HGP during insulin-induced hypoglycemia. HGP during recovery from insulin-induced hypoglycemia to euglycemia.

Exploratory Objectives and Endpoints	
Objective	Endpoint
To evaluate the effects of MBX-2982 upon fasting and postprandial glucagon, GLP-1 and GIP concentrations in subjects with T1D relative to placebo treatment.	Fasting and post-prandial levels of glucagon, GLP-1 and GIP
To evaluate the effects of MBX-2982 on patterns of glycemia determined by continuous glucose monitoring in subjects with T1DM relative to placebo.	Continuous glucose monitoring (CGM) indices of glycemic control including hypoglycemia (percent of time < 70 mg/dL, < 54 mg/dL), hypoglycemic events, mean glucose, percent of time 70-180 mg/dL, percent of time > 180 mg/dL, percent of time > 250 mg/dL, glycemic variability
To evaluate the pharmacokinetic profile of MBX-2982 in subjects with T1DM.	MBX-2982 plasma levels.

4 STUDY DESIGN

4.1 OVERALL DESIGN

[figure not shown]
This research will be carried out as a placebo-controlled, double-blinded, within-subject, cross-over phase 2a study.

Overview of the study design:

- In randomized order, (Latin square, randomly assigned to placebo-active and active-placebo periods) and in a double-blinded manner, the T1DM subjects will receive 14 days of daily dosing with MBX-2982 (or placebo), taken at the same time each day after breakfast. The last dose of treatment/placebo will be given when the glucose tracer infusion for the euglycemic/hypoglycemic-glucose clamp is started.
- T1DM subjects will undergo two euglycemic-hypoglycemic clamps (induction of controlled hypoglycemia by an insulin infusion), using a within-subject cross-over design, with the two clamps separated by approximately four weeks, that is, two weeks of drug washout followed by two weeks of treatment with the alternative therapy.
- After completion of the first clamp study, participants will not receive any study medication for two weeks (washout phase) and then begin 14 days of the other arm (placebo or MBX-2982) in a double-blinded manner, followed by a repeat euglycemic-hypoglycemic clamp study. During treatment on each arm and during wash out phase, a blinded CGM will be used to assess daily and nocturnal patterns of glycemia.
- On the day preceding a clamp study, while admitted to the research unit, a standardized meal test will be used to assess fasting and postprandial glucagon, GLP-1 and GIP secretion.

Overview of the hypoglycemic clamp: Regarding the procedures of the clamp, there will be an initial euglycemic run-in phase of the clamp, (~85 mg/dL), followed by induction and maintenance of hypoglycemia (target 50 mg/dL), and then a phase of recovery from hypoglycemia. Throughout, glucagon, other counter-regulatory hormones, and hepatic glucose production will be measured. Healthy, non-diabetic control subjects will be studied on a single occasion and will not receive pre-treatment

medication or placebo; they will be studied to establish “normal physiological responses” for comparison to drug and placebo treated responses in T1DM.

